The goal of this prospective, non-randomized, pilot quality improvement study is to evaluate how CGM usage with and without remote monitoring capabilities affects glucose variability, A1C control, and patient-related outcomes compared to non-CGM use in pregnancy among women with T1DM. This study may lead to further investigations about the role of mobile phones and handheld devices (such as iPod touch) for T1DM self-care in pregnancy.

The Barbara Davis Center (BDC) Adult Clinic follows ~3,000 patients with T1DM. [name], MPH is this study's Principal Investigator and the director of the Pregnancy and Women's Health Clinic at the BDC, which includes an extensive multidisciplinary team (physician's assistant, nurse practitioner, registered nurses, certified diabetes educators, registered dieticians, and a social worker). The BDC Pregnancy and Women's Health Clinic has all the necessary resources to perform such a trial. Moreover, the investigators have extensive experience conducting clinical trials, including trials during pregnancy.

Primary Objectives:

The primary objectives of this pilot study are to improve maternal glucose management, to assess the role of CGM usage either alone or with remote monitoring capabilities (Share™) and changes detected by the hypoglycemia fear questionnaire among women with T1DM associated with pregnancy.

Secondary objectives:

1. Assessment of remote monitoring capabilities of followers (Share™ usage) that lead to interventions for hypoglycemia and hyperglycemia that affect subjects wearing CGM.
2. Reduction in A1C from baseline to 3 months with maintained control at 6 and 9 months.
3. Assess progression or stability of diabetes complications (retinopathy, nephropathy).
4. Assess effects of CGM usage on maternal and fetal health outcomes (eclampsia/pre-eclampsia, live birth rates, birth weight, neonatal hypoglycemia, and other similar measures).

Research Design:

What do we intend to do?

We intend to execute a single-center, prospective, non-randomized, 'open-label,' investigator initiated pilot study evaluating the effect of CGM usage with or without remote monitoring capabilities on women with T1D throughout pregnancy and compare outcomes to women who do not use a CGM during pregnancy. We also intend to ask a main follower for each woman about his/her knowledge of extreme glucose values among subjects and interventions on a subject's behalf. See Figure 1 for study design.

How are we going to do the work?

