The primary study population will consist of women at the BDC in the pre-conception and early gestational periods that are eligible for this pilot investigator-initiated CGM QI Project. Subjects will be women intending to become pregnant or within the first 13 weeks of gestation, 18 years of age or older, using MDI or CSII therapy, with any A1C level, and willing to participate in the study. There is also a no CGM comparison group of women who were pregnant around the time study enrollment began and earlier who were patients at the BDC and whose data are available retrospectively through the electronic medical record system. The secondary study population will be designated followers of pregnant patients at the BDC. Followers will be family members or friends of pregnant subjects who are willing to participate in the study.

How are subjects being recruited into the study?

Subjects will be recruited from the BDC Pregnancy and Women's Health clinic for screening, as well as the BDC Adult Clinic. During pre-conception counseling visits, women will be approached about participating in the study (if eligible). We will maintain a list of women intending to conceive within the next 6 months, ask women to come in for a pregnancy visit as soon as pregnancy is confirmed, and stratify women into 1 of 3 groups described below. If after 6 months a woman on the list has not yet come in for a pregnancy visit, we will contact her to inquire if she still plans to conceive (keep subject on the list) or not (remove from list).

Women who have their first pregnancy visit at the BDC at 13 weeks of gestation or less will be screened for the study. If eligible and interested in participating, after signing the informed consent, women will be stratified to either CGM use alone (Group 1) or CGM use with Share™ (Group 2). As Share™ requires specific device use, Group 1 subjects will be women who do not have an iPhone, iPad, or iPod touch or whose main follower does not have an iPhone, iPad, or iPod touch. Group 2 subjects will be women who have an iPhone, iPad, or iPod touch and whose main follower also has an iPhone, iPad, iPod touch, or other compatible device for downloading the Follower app. If eligible to participate but not interested in using a Dexcom CGM, women will be invited to sign informed consent so that we may follow their

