After screening, subjects assigned to Group 2 will be asked to designate a main follower and up to 4 other followers who will be allowed access to view glucose trends, to receive low sensor glucose alerts, and to receive high sensor glucose alerts for the subject. After screening, subjects assigned to Groups 1 or 3 will be asked to designate a main follower with whom she shares time and/or information about her diabetes care and who may intervene on her behalf should a need arise (e.g., provide glucagon for severe hypoglycemia, or suggest going to the hospital for extreme hyperglycemia). Main followers who sign informed consent, which will be obtained in person or by phone, will be asked to fill out a brief questionnaire once per month inquiring about the frequency of viewing information about glucose trends, receiving alerts or information about extreme low and high glucose values, and acting upon aforementioned data to assist the subject. The main follower can fill out the Follower Questionnaire on paper or s/he can receive the follower questionnaire electronically through REDCap if s/he has a working e-mail address (see *Data Collection Tools* section for details).

Description of Mobile Technology:

Subjects in Group 2 will be trained on the use of Dexcom G4 Platinum® CGM system with Share™. This is a bluetooth low energy secure wireless communication system that allows remote viewing of sensor glucose levels, trends, and data between the person with diabetes wearing the CGM and her designated family members or friends. The followers can additionally receive alerts (alarms) for pre-specified low sensor glucose and high sensor glucose values. The person with diabetes can also designate herself as a follower to allow access to data through the approved devices. This technology is currently only available for use with Apple iPhone®, iPad, or iPod touch®. Followers have to have access to a device (smart phone) that allows download of the Dexcom Follower app. We will not provide iPhones, iPads, or iPods to subjects or followers for this study.

Visit Descriptions:

Screening, Visit 1 (Week 0):

The study will begin with a screening visit either during a pre-conception counseling visit or within the first 13 weeks of gestation: Visit 1, (Week - 0). All subjects meeting inclusion/exclusion criteria will be invited to sign informed consent, which will be obtained at this study visit.

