Visits 3 through 13 (Weeks 5 to 40):

Subjects will come to the BDC for routine clinical care at least once per month for the duration of the pregnancy (through gestational week 40, though some women deliver up to 42 weeks gestation) and for continued study participation. Per routine clinical care, we will screen for diabetic neuropathy on physical exam, thyroid disease (TSH blood draw), and kidney disease (24-hour urine protein with creatinine) at least once each trimester. Also per routine clinical care, women will be asked to get a dilated retinal eye exam each trimester and to provide the BDC with a copy of the provider's report of each exam.

Subjects in Groups 1 and 2 will receive 4 new sensors per month, but may choose to get 2 sensors twice a month instead, at study visits. Use of acetaminophen-containing medications like Tylenol® during sensor wear may affect device performance, therefore we will ask subjects to keep a log of each time these medications are used. We will ask subjects at each monthly visit whether she used acetaminophen-containing medications during the previous month and when. Followers will be administered a brief questionnaire at the beginning of every month inquiring on the frequency of low alerts, high alerts, viewing glucose trends, and actions they may have taken on behalf of the subjects because of the above (see Table 2 and *Follower Questionnaire* for details). On source documents, we will also record how often subjects required an intervention for low or high glucose values within the previous month, and the nature of the interventions. If in Group 2, we will keep source documentation about interventions resulting from a Share™ alert within the previous month.

Data on all pregnant subjects for medications, vital signs, height/weight, insulin doses, glucometer downloads, insulin pump downloads (if applicable), and CGM downloads (if applicable) will be collected at least once per month and as often as every week. All subjects will be asked to collect a 7-point profile for SMBG measurements (blood glucose measurements before meals, 2 hours after meals, and at bedtime) along with meal insulin dosing for 1 week once per trimester (see SMBG Questionnaire). A1C will be measured once per month. Subjects will be asked about updated concomitant drugs and any AEs that may have occurred. Each subject will be given a hypoglycemic fear questionnaire.

Visit 14 (Weeks 44 to 52):

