Appendix E

Follower Questionnaire

Subject ID: _____

Clinic Visit: (dd/mmm/yyyy) : _____ / _____ / _____

Gestational Age of Pregnant Participant:

4 to 8 weeks 8 to 12 weeks 12 to 16 weeks 16 to 20 weeks 20 to 24 weeks

24 to 28 weeks 28 to 32 weeks 32 to 36 weeks 36 to 40 weeks 40 to 42 weeks

4 to 12 weeks post-partum

LOW GLUCOSE QUESTIONS

How many times were you alerted to low glucose levels this month?

Never 1-5x mo 1-5 x weekly Daily More than 1 x daily N/A

Did you intervene to help your pregnant partner with low glucose levels this month?

Yes No

If yes, how often?

Never 1-5x mo 1-5 x weekly Daily More than 1 x daily N/A

If yes, what was the nature of the intervention? Check all that apply.

Gave glucose tablets/gel Gave glucagon injection

Gave food or drink with carbohydrates Called health care provider

Checked blood glucose level Called emergency services (like 911)

Other (Please describe: _____)

How many times did your pregnant partner's low glucose levels interfere with her daily activities this month?

Never 1-5x mo 1-5 x weekly Daily More than 1 x daily N/A

HIGH GLUCOSE QUESTIONS

How many times were you alerted to high glucose levels this month?

Never 1-5x mo 1-5 x weekly Daily More than 1 x daily N/A

Did you intervene to help your pregnant partner with high glucose levels this month?

Yes No

If yes, how often?

Never 1-5x mo 1-5 x weekly Daily More than 1 x daily N/A

If yes, what was the nature of the intervention? Check all that apply.

Gave insulin shot Checked ketone level

Gave insulin through an insulin pump Called health care provider

Checked blood glucose level Called emergency services (like 911)

Other (Please describe: _____)

How many times did your pregnant partner's high glucose levels interfere with her daily activities this month?

Never 1-5x mo 1-5 x weekly Daily More than 1 x daily N/A

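### The Follower Questionnaire lacks the promised trend-viewing item and does not record the alert route, so Share use is only partly measurable in Group 2 and not identifiable in Group 1

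*Combined protocol and SAP*

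**What the plan says.** **What the form is meant to ask.** The section on the schedule of events for the follower group says consenting main followers complete a monthly questionnaire "inquiring about the frequency of viewing information about glucose trends, receiving alerts or information about extreme low and high glucose values", and also whether they acted on what they learned. The section on Visits 3 through 13 repeats this and refers to the form for details: "inquiring on the frequency of low alerts, high alerts, viewing glucose trends, and actions they may have taken on behalf of the subjects".

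**What the form asks.** Appendix E has a low-glucose block and a high-glucose block. The first opens with "How many times were you alerted to low glucose levels this month" and the second ends with "How many times did your pregnant partner's high glucose levels interfere with her daily activities this month".

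**What the data are for.** Secondary objective 1 is "Assessment of remote monitoring capabilities of followers (Share™ usage) that lead to interventions for hypoglycemia and hyperglycemia" affecting women who wear CGM. The Statistical Analysis Plan compares followers' low-alert, high-alert and intervention frequencies between arms with t-tests. It also tests Dexcom alone against Dexcom with Share.

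**Other records of Share or of interventions.** At Visits 3 through 13, "If in Group 2, we will keep source documentation about interventions resulting from a Share™ alert within the previous month". For all prospective women, "we will also record how often subjects required an intervention for low or high glucose values within the previous month", without reference to Share.

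**Who is in Group 1.** Under the recruitment section a woman enters Group 1 if she herself has no Apple device, or if she is a woman "whose main follower does not have an iPhone, iPad, or iPod touch". The Visit 2 section says main followers in Groups 1 and 3 are to learn of glucose values by contact with the woman and not through a device. Follower participation is optional in every group.

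**The concern.** The protocol describes a direct measure of how followers engage with the woman's glucose data, and the instrument meant to collect it does not contain it. The alert items are the nearest substitute, but they pool two different events: an alarm from an app, and being told by the woman. By design only Group 2 followers have the first route. A difference between arms in alert frequency could therefore be a by-product of the app's alarms, a difference in glucose extremes, or a difference in how much women tell their followers.

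The other gap is in Group 1. The protocol takes it that these women are not followed remotely, but describes no check. Without one, the Dexcom-alone arm cannot be confirmed as Share-free. The pilot is meant to inform a larger randomized study, so knowing whether Share was used, and by whom, is one of its more useful products.

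**Working it through.** No power or usage figure is stated on this point, so the check is mainly a comparison of texts.

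**1. Promised content against form content**

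| Content promised in the follower schedule | Item in Appendix E |
|---|---|
| Viewing glucose trends | None |
| Alerts or information about extreme values | Yes: frequency, separately for low and high |
| Acting on the information | Yes: yes/no, frequency, nature, separately for low and high |

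Two of three contents are covered. The form's remaining items, on interference with daily activities, do not substitute for viewing. Appendix E is printed in full, so this is not a gap in the text. The Visits 3 through 13 section lists viewing separately from low and high alerts, so it was not meant to be absorbed into the alert items.

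**2. What the alert item can show**

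- Group 2 main followers can be alerted by app or by contact. Those in Groups 1 and 3 are meant to be alerted by contact only. The item offers no choice of route.
- Appendix A says sharing works only while the app is open, the woman can change access to the trend graph, and the follower can change notification settings. A Group 2 answer of Never could therefore mean no extreme values, alerts turned off, or the app closed.
- Only the main follower is surveyed, while Group 2 women may have up to 4 others.

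**3. Share-specific records described**

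| Group | Record |
|---|---|
| 2 | Interventions that resulted from a Share alert |
| 1 | None |

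Even in Group 2, a month of Share use without an intervention leaves no Share-specific entry.

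**4. Can Share be used in Group 1?**

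- The group rule has two branches. Under the first, the woman has no Apple device and, by the protocol's description of the technology, cannot run Share. Under the second, she may own one and only her main follower lacks it.
- Women assigned to CGM may use a personal G5, including one paired with an iPhone, and Appendix A allows 5 followers. Someone other than the main follower could therefore follow a second-branch woman.
- Mobile usernames are collected from personal G5 users with an iPhone, but no use of them as a sharing log is described.

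**5. Scale**

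Anticipated allocation: 10 + 20 + 10 = 40, which matches the recruitment ceiling. One Group 1 woman using Share is 1/10 = 10% of that arm; two are 2/10 = 20%. The documents give no basis for saying how many there would be.

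**The case against.** The case on the other side is substantial, and most of it stands as a limit on the claim.

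- **Group 2 is not unmeasured.** Monthly alert frequency and the record of Share-triggered interventions give some evidence of delivery. A reader might infer that Share exposure is not measured at all, or that secondary objective 1 is left without data. The documents do not support that: the objective concerns Share usage leading to interventions, and those are recorded.
- **No planned analysis loses its variable.** The Statistical Analysis Plan does not list viewing frequency. This stands, but the alert comparison it does list is affected by the missing route.
- **Crossover is possible only for a subset.** Women without a device cannot share, non-Dexcom CGM users also enter Group 1, only Group 2 is trained on Share, and the documents do not say that the G4 units supplied to Group 1 can share.
- **The monthly subject source documents are not reproduced.** They might contain a Share question. The supportable statement is that the protocol describes none.
- **A null result would be ambiguous anyway.** This is a small, non-randomized pilot with no formal power and allocation by device ownership. Perfect usage data would not allow a null to be attributed to Share being ineffective.

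A reader might also put a figure on dilution, taking the retained effect as use in Group 2 minus use in Group 1. Assuming 70–90% and 10–30%, this runs from 0.70 − 0.30 = 0.40 to 0.90 − 0.10 = 0.80. Those rates appear nowhere in the documents, and the formula assumes one constant effect of yes/no use. It is purely an illustration.

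None of this removes the mismatch between the protocol text and its form, or the pooling of alert routes in a planned comparison.

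**Conclusion.** The point holds in a limited form. One of three promised contents of the monthly follower form is absent. The alert items mix two routes in a comparison the plan intends to test. Delivery of Share in Group 2 can be judged only partly and indirectly, from optional forms completed by one follower of up to five and from interventions after Share alerts. Share use in Group 1 would not be identified by any record described.

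This rests on Appendix E being the form in use and on the source documents containing no more than the protocol says. The extent of Group 1 use is unknown, so no bias or loss of power can be quantified. The gap weakens interpretation of the Share comparison and what the pilot can pass on to a larger study. It does not invalidate the study. It should be corrected, because the correction is cheap and missed months cannot be recovered.

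**What to change.** 1. Add to Appendix E the trend-viewing frequency item that the protocol already describes, on the form's existing response scale.
2. Split the low-alert and high-alert items by route: Share/Follow app, or contact with the woman. Report the planned comparison of alert rates by route.
3. At monthly visits, record for Groups 1 and 2 whether anyone is receiving the woman's CGM data remotely.
4. Keep the analysis by assigned group. Report Share use descriptively by group. Label any comparison by actual use as exploratory, because use is self-selected and the groups are small.

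**Cost:** a minor form amendment, a few tick-boxes at existing monthly contacts, and slightly more data entry. Forms already completed cannot be recovered, so the report should state from which date the new items were collected.
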